## 5.2. Applicable Regulations

All products and devices used during this pilot are CE-certified and commercially available products. The German Medical Product Law (= Medizinproduktgesetz, MPG) does not apply to the pilot according to § 20 MPG. A data protection vote for the pilot was requested from the local data protection authority on the 12.01.2016 and a positive data protection vote was received on the 10.03.2016. It was also necessary to obtain an ethical vote from the local ethics commission. For this purpose, all relevant questionnaires and the overall procedure had to be presented to the consortium of the ethics committee. An appointment for the presentation was requested at 10.01.2016 and the actual presentation was given on the 17.02.2016. Results from the ethics commission were received on 11.03.2016, with a request for minor amendments. The revised documents were returned to the ethics commission on the 14.03.2016. The final positive ethical vote is expected at the end of March 2016.

### 5.2.1. Data Protection

The privacy protection regulations are determined by federal law. All data related to the users will be registered pseudonymously. Each participant is distinctively marked by a two digits number, which is assigned to her during the registration process. The coordinator of the study keeps a confidential list of users in which the data is linked to the full name of the user. Only the study coordinator will have access to this list.

## 5.3. Main Results of Former Clinical Studies

Due to the fact that this is a pilot study, no further investigations in the areas to be investigated have been made. Within this pilot, a pre-test will be conducted to optimize the evaluation instrument.

D8 3 1 Piloting Validation II Hospital.docx	Document Version: 1.0	Date: 2016-03-31	Status: For Approval	Page: 26 / 34
http://www.alfred.eu/		Copyright © ALFRED Project Consortium. All Rights Reserved. Grant Agreement No.: 611218		

## 5.4. Recruitment and Screening

The recruitment process for the pilot started on the 05.01.2016 and ended on the 14.03.2016. Subjects were recruited through announcements in resident physicians' offices, pharmacies, senior activity centres, and existing contacts of project partner CHA. Overall, 380 seniors were telephonically screened for inclusion and exclusion of the pilot. 64 subjects met the all relevant criteria.

### 5.4.1. Inclusion and Exclusion Criteria

The following section will describe the inclusion and exclusion criteria which were used for the users of the pilot.

Inclusion criteria (pretest and main study):

- Age > 65 years
- Existence of a participant's information and a signed acceptance
- Presence of LBP for at least 6 weeks during the 12 month

Excluding criteria (pretest and main study):

- Heavily affective or cognitive diseases
- Acute LBP
- Participation on another intervention study
- Presence of a legal guardian
- Immobility
- Recent major chirurgical intervention
- Acute herniated disc
- Tumorous affection of the spine

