## 2. Low Back Pain

Throughout society, low back pain (LBP) is a common medical problem and often recurrent. During their lifetime, 60-80% of the populace will experience LBP and up to 86% of these people will have a second or more episodes at some point [FWW10]. Especially chronic low back pain is hence a large socioeconomic burden which seems to be growing, in spite of technological advances in diagnostics and intervention. The purpose of this second chapter is to look at therapeutic interventions, exercises and biofeedback training, available for chronic non-specific LBP, while keeping models of pathology in mind.

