### 3. Etiopathology

Low back pain (LBP) is commonly defined as pain, muscle tension or stiffness localized below the costal margin and above the inferior gluteal folds, with or without sciatica (leg pain). LBP can be either specific or non-specific. Symptoms that are caused by a specific pathophysiologic mechanism are described as being specific LBP, i.e. inflammation, infection, hernia nuclei pulposi (HNP), osteoporosis, rheumatoid arthritis, fracture or tumor. The majority of patients, about 85%, however will suffer from nonspecific LBP, defined as having no identifiable cause or pain of unknown origin [HS08].

Low back pain can be classified by duration: an episode of less than 6 weeks being acute LBP, between 6-12 weeks subacute LBP, and episodes that are lasting longer than 12 weeks chronic LBP. Even though studies suggest that more than 90% of patients will stop consulting a physician within 3 months of initial LBP complaints, they will still be experiencing pain and disability up to one year afterwards [Cro98]. Even more so, studying the long-term course Hestbaek et al. found recurrence rates to be 50% after one, 60% after two, and 70% after three years [HLM03].

Examining occurrence and chronicity factors as well as the possible underlying pathology of nonspecific low back pain is therefore crucial for developing treatment and prevention strategies.

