### 3.2.1. Specific Low Back Pain

Specific LBP etiology presents a small portion of total prevalence in patients. The most common specific cause is found to be compression fracture (4%), followed by spondylolisthesis (3%), herniated disk (1-3%), neoplasia (0.7%), Ankylosing spondylitis (0.3%), cauda equina syndrome (0.04%) and least common infection (0.01%) [DRK92].

Atlas et al. (Table 2) identified three different major groups of LBP origin. Mechanical LBP, which in part also represents nonspecific LBP, non-mechanical spine disease, and visceral disease.

Mechanical LBP includes specific as well as non-specific causes but even when specific imaging findings such as degenerative disk disease, spondylolysis, spondylolisthesis or osteoporosis are found in combination with LBP, it may be difficult or impossible to establish if the finding is the cause of the symptoms. This topic, however, will be dealt with in depth further on.

To identify an even less common non-mechanical spine disease, namely neoplasia, infection or inflammatory arthritis, most clinical practice guidelines provide “red flags” that indicate the need for further screening. In a recent systematic review, that analysed diagnostic accuracy of various red flags for spinal fractures and spinal malignancies older age, prolonged corticosteroid use, severe trauma, and presence of a contusion or abrasion increased the likelihood of spinal fracture [Dow11], but for the likelihood of spinal malignancy, the actual non-mechanical spine disease, only a history of malignancy had an effect. Other sources [AD01, KT07] include unexplained weight loss - defined as more than 10 pounds in the preceding 6 months - and old age that could indicate a malignant etiology, though without stating diagnostic accuracy.

Visceral disease is the least common LBP origin and is often accompanied by other symptoms, i.e. an acute pancreatitis that will also cause abdominal pain and nausea, symptoms that are rarely associated with LBP.

Since causal therapy options for specific LBP exist and the purpose of this review is to examine nonspecific low back pain, further literature research concerning diagnostics and therapy was not undertaken.

Table 2: Differential Diagnosis of Low Back Pain [Dey86]

Mechanical Low Back Pain	Non-mechanical Spine Disease	Visceral Disease
Lumbar strain or sprain	Neoplasia	Pelvic organs
- Degenerative disease	- Metastatic carcinoma	- Prostatitis

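### The 5.4.1 exclusions leave out spinal fracture, so a person over 65 with a symptomatic vertebral fracture and pain beyond 6 weeks is eligible as written

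*Combined protocol and SAP*

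**What the plan says.** The LBP criterion in section 5.4.1 is "Presence of LBP for at least 6 weeks during the 12 month", alongside age over 65 and consent. The exclusions that bear on the spine are acute LBP, acute herniated disc and tumour of the spine. Immobility and recent major surgery are also excluded. Spinal fracture, spinal infection, cauda equina syndrome and inflammatory spine disease are not mentioned.

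Section 3 classifies LBP by duration, with "an episode of less than 6 weeks being acute LBP". Section 3.2 says that serious underlying pathology should be identified so that contraindicated treatment is avoided. Section 3.2.1 gives compression fracture as the most common specific cause, at 4%, and reports from a systematic review that "older age, prolonged corticosteroid use, severe trauma, and presence of a contusion or abrasion increased the likelihood of spinal fracture".

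Section 5.4 says that 380 people were screened by telephone and 64 met the criteria. Section 5.6 places consent, a physical examination and questionnaires at the first visit, followed by randomisation of 60. The listed measures include static trunk endurance and spinal mobility, but no history of spinal diagnoses. Section 5.6.1 states that the inclusion and exclusion criteria ensure that only physically and mentally suitable people take part.

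**The concern.** The background chapters and the eligibility list do not fit together. The background ranks fracture above the other specific causes and says that age raises its likelihood. The eligibility list then selects on age and excludes two less frequent specific causes, but not fracture. No reason is given.

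At stake is the safety of an individual participant. Someone with a known, painful vertebral fracture could take the trunk endurance and mobility tests and then be randomised to 10 weeks of training, without any written rule being broken. The plan relies on the criteria to prevent this kind of entry.

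**Working it through.** The plan states no figure on this point, so there is none to reproduce. The check sets the rules against one hypothetical person, then looks at what the fix could cost in numbers.

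**Step 1: pass the person through 5.4.1.** Take someone aged over 65 with a known symptomatic vertebral fracture and 8 weeks of pain (an assumed example).

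- Age over 65: met.
- LBP for at least 6 weeks within 12 months: met, since 8 ≥ 6. The criterion does not ask for the cause.
- Acute LBP: does not apply. Section 3 sets acute at under 6 weeks, and 8 weeks falls in its subacute band of 6 to 12 weeks.
- Acute herniated disc and spinal tumour: do not apply.
- Immobility and recent major surgery: do not apply unless the person happens to have them.

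The person is eligible. A fracture with less than 6 weeks of pain would normally be caught as acute LBP, so the gap is fracture with longer pain.

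**Step 2: compare the exclusions with the ranking in 3.2.1.**

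| Specific cause | Share in 3.2.1 | In 5.4.1? |
|---|---|---|
| Compression fracture | 4% | No |
| Spondylolisthesis | 3% | No |
| Herniated disc | 1–3% | Yes, if acute |
| Neoplasia | 0.7% | Yes, if spinal |
| Ankylosing spondylitis | 0.3% | No |
| Cauda equina syndrome | 0.04% | No |
| Infection | 0.01% | No |

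The ranking describes LBP patients in general. It shows the order of causes, not the rate in this older and already screened group.

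**Step 3: look for a later step that would catch the person.** The measures listed in 5.6 and the items in 5.6.3 (fall risk, balance, strength, endurance) include no question about spinal diagnoses. Section 5.6.1 asks participants with uncertainties to see their own physician, which depends on the participant having and raising the doubt.

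**Step 4: cost of the fix in participants.** Spare people = 64 - 60 = 4, so 60 can still be randomised if no more than 4/64 = 6.25% are removed. With X ~ Binomial(64, p), the chance of losing more than 4 is P(X > 4):

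| Assumed share removed, p | P(X > 4) |
|---|---|
| 2% | 0.009 |
| 4.35% | 0.146 |
| 8% | 0.588 |
| 10% | 0.780 |

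The 4.35% is the sum 4 + 0.3 + 0.04 + 0.01 from 3.2.1, with ankylosing spondylitis standing in for inflammatory spine disease. The other values are assumptions. Because the fix removes only recent, symptomatic or suspected fractures, not all compression fractures, the true share may be below the general figure. Because the group is older, it may be above.

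**The case against.** The strongest reply is that harm is not shown. No part of the document says that bridging or static trunk tests endanger a person with a fracture, and the contraindication example in 3.2 is manual therapy. Sections 5.6.1 and 5.6.2 add trained supervision, adaptation to the individual, breaks and the right to stop. This stands, and it limits the point to a modest safety gain. It does not remove the point, since staff can adapt only to a diagnosis they know about.

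A second reply is that a history may already be taken. The content of the physical examination is not described, the telephone script is not reproduced, and the papers shown to the ethics commission are not in this document. That also stands: one cannot say that nobody asks about fracture. But an answer would trigger no exclusion, because no criterion covers it.

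Three stronger readings are tempting and are not supported.

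- A reader might infer that entry must be limited to non-specific LBP, because section 2 looks at "exercises and biofeedback training, available for chronic non-specific LBP" and 3.2.1 says that "the purpose of this review is to examine nonspecific low back pain". These sentences set the scope of the literature review, not of eligibility. For degenerative disc disease, spondylolisthesis or osteoporosis found together with LBP, 3.2.1 also says that "it may be difficult or impossible to establish if the finding is the cause of the symptoms", so the restriction would be hard to apply.
- A reader might multiply 4% by the sample size to count expected fractures. The rate in this filtered group is not given, so the product would not estimate anything in this trial.
- A reader might want everyone with a history of trauma, corticosteroid use or malignancy deferred. How many people this would hold back is unknown. If it removed 10%, the chance of falling below 60 would be 0.78.

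**Conclusion.** The point holds in a limited form. As written, 5.4.1 admits a person over 65 with a symptomatic spinal fracture and pain of 6 weeks or more, and on this point the suitability assurance in 5.6.1 goes further than the criteria do. This is a rule that admits a person it should stop, not only a missing detail.

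The change is a cheap improvement with a modest patient-safety gain. The conclusion rests on the section 3 definition of acute LBP being the one meant in 5.4.1, and on no unlisted rule excluding fracture. The number of people affected cannot be estimated from the document. The point does not say that the exercises are harmful or that anyone unsuitable was enrolled.

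**What to change.** Add one line to the 5.4.1 exclusions: *known or clinically suspected recent or symptomatic spinal fracture, or known spinal infection, cauda equina syndrome or active inflammatory spine disease*. State that old healed fractures, stable spondylolisthesis and degenerative findings remain eligible.

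At the existing first visit, after consent and before the trunk endurance tests, mobility tests and randomisation, ask directly about these diagnoses. Anyone who reports one is not tested or randomised unless their physician rules it out.

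The cost is a few questions and a short ethics amendment. Section 5.2 says that revised papers went back on 14.03.2016 and that the final vote was still expected, so the amendment would reopen a file close to approval. Recruitment has closed, so slightly fewer than 60 may be randomised. The margin is at most 4, because the document does not say whether pre-test users come from the 64. No stated power figure depends on reaching 60.

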## 5.5. Pretest

After the screening process, there will be a pre-test of all involved devices and questionnaires with the older adults in order to ensure an optimal process of the pilot. During the pre-test, users are asked about problems with handling the questionnaire and the instructions and are asked for potential improvements. All comments will be protocolled anonymously by a member of the pilot team.

The critique of the elderly from the pre-test will be taken into consideration and serve as a basis to adapt the questions of the actual pilot in order to warrant maximal comprehensibility.

Changes can contain:

- erasing or reformulating single questions of the questionnaire
- adding choices
- changing words chosen for the instruction
- changing questions of the questionnaire about frame data, healthy behaviour and ratings to improve and estimate the usability
- changes in schedule
- changes in the instructions

D8 3 1 Piloting Validation II Hospital.docx	Document Version: 1.0	Date: 2016-03-31	Status: For Approval	Page: 27 / 34
http://www.alfred.eu/		Copyright © ALFRED Project Consortium. All Rights Reserved. Grant Agreement No.: 611218		

## 5.6. Methodology Pilot 2

At least 24 hours before the actual start of the pilot, the previously screened older adults will receive the participant information, either by Email or via postal service. This information will also contain date and time of the first visit of potential participants of the pilot. At the beginning of the first visit, potential participants will receive the opportunity to clarify any questions relevant to the pilot with the team of the pilot. Once all questions are resolved and the potential participant agrees to enrol in the study, informed consent will be signed and the physical examination will be performed and questionnaires will be filled out by the included subjects.

Each participant receives a unique participant's number by the study personnel. Finally the 60 participants will be randomized either to the group "conventional back training" (CR, 20 participants) or to the group "conventional back training with biofeedback" (CRB, 20 participants), or to the control group (CG, 20 participants).

The following data of the participants will be collected:

- Sociodemographic data to enable clustering the participants (age, sex, educational background)
- Functional questionnaire "Hannover Rücken"
- Oswestry Disability Index
- Static measures of the muscular endurance of the muscular erector spinae of the lateral and straight abdominal musculature
- Spinal mobility referring to Schober-Ott
- Fingertip-floor-distance
- Four Square Step Test
- Five Times Sit to Stand Test
- Visual analogue scale for dorsal pain
- Pittsburgh sleeping quality index
- Standardised questions to health behaviour

Afterwards, a short training on how to handle the ALFRED Back Trainer and a demonstration of the exercises future appointments are scheduled.

### Visit 2-25 Intervention group with supervision

The study contains exercises which improve muscular activity and are of medium intensity. The exercises to prevent LBP are conducted on the floor with either a sport mattress (CR) or commercially available Nintendo Wii Balance Boards (CRB) which will provide biofeedback. The exercises will take place in a lying position with the subjects lying on their back. The study wants to examine if the additional employment of biofeedback (CRB) with the same amount of training as in the conventional back training (CR) will lead to different preventive factors of LBP. Furthermore, it shall be examined if the CRB yields additional positive training effects compared to the CR in relation to muscular strength, execution of everyday life activities, balance and LBP. Secondary, it shall be examined if a different acceptance level between the two groups occurs.

The participants of both groups will be trained for a total period of 10 weeks. Users train 2 days a week. Each session takes 40 minutes and consists of a short warmup and 30 minutes of training. The exercises which have to be performed by the subjects are taken

D8 3 1 Piloting Validation II Hospital.docx	Document Version: 1.0	Date: 2016-03-31	Status: For Approval	Page: 28 / 34
http://www.alfred.eu/		Copyright © ALFRED Project Consortium. All Rights Reserved. Grant Agreement No.: 611218		

from the manual of the federal association of German back schools. The training program was compiled by a certified trainer and a physiotherapist. Additionally, in order control the vital signs of the participants, there is a possibility to wear the ALFRED sensor T-shirt which can measure body temperature, breathing rate and heart rate. The biofeedback data of the CRB group are presented to the participants on commercially available Samsung Galaxy Tab 2 Tablet, which is mounted on a tripod. The control group will receive the results of their health assessments by mail, after the end of the study.

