## 4. Conclusion

Based on the findings of this literature research, a specific exercise regime was developed to explicitly improve the clinical stability of the lower back. The exercises are designed to strengthen the lumbar multifidus muscles which are the major contributor to lumbar stability. The exercises which will be used are so called “bridging exercises”. These exercises are executed while the users are lying on their backs, hips flexed at a 45 degree angle and knees at a 90 degree angle. From this position, the user has to lift her pelvis off the ground such that lower back, pelvis and thigh form a straight line. This position has to be actively held by the user for a period of 20 seconds, before the pelvis can be lowered again in a steady and controlled manner to the initial position (Figure 4).

As previously mentioned, bridging exercises are able to produce high activities of the stabilizing muscles of the spine, especially if they are combined with motions of the extremities of the user (Figure 5). In addition to the benefits of bridging exercises, biofeedback training for the lower back could help to address the localized muscles mass reduction in persons with LBP and therefore reduce the currently high recurrence rates of LBP. Additionally to the benefit of bridging exercises to the lumbar spine, the ALFRED Back Trainer application can provide users with biofeedback information which is displayed to the user on a regular, commercially available tablet computer mounted to a tripod. The main difference of the ALFRED Back Trainer and standard bridging exercises is that the user will additionally lie on two Nintendo Wii balance boards. The balance boards will be horizontally placed under the shoulders and the feet of the user and give feedback of the motion of the user during the bridging exercise (Figure 10). The stabilizing muscles of the spine are by nature very small in size and are not able to produce large motions. For this reason it is very hard to see for the human eye whether or not the local stabilizing muscles are activated equally strong at both sides of the spine during the bridging exercise. Symmetrical activation of the local spinal stabilizers however is necessary to restore the muscle balance in the lower back area in order to reduce the recurrence rates of LBP, increase spinal stability and therefore reduce LBP.

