## 5. Pilot 2: Procedure

This section will describe the goal of the pilot, applicable regulations, examinations measures, recruitment strategy, pretest procedures, procedure of the main pilot, predicted therapeutically benefits for the users and for future diseased person groups, potential risks and risk management, exit criteria, inclusion/exclusion criteria, documentation details and data protection.

Overall, 60 users will be randomized into three different groups to the pilot. The first group “conventional back training” (CB, 20 users) will receive stabilizing exercises for the lower back, according to the principles from the literature discussed in Chapter 2 and 3 of this document. The second group (CBB, 20 users) will perform identical exercises as the CB group, but with the additional perceived benefit of biofeedback training. Biofeedback will allow the users to visually observe their motions during the exercises on a commercially available tablet PC which will be mounted to a tripod. While the users are lying on two commercially available Nintendo Wii Balance Boards (one underneath their shoulders and one underneath their feet), they can see their body motions during the exercises on the tablet screen. The hypothesis of the pilot is that the additional use of biofeedback during stabilizing exercises for the lower back will lead to increased LBP reduction, higher functionality during activities of daily life, increased muscle strength and improved sleep quality. The third group (C, 20 users) will serve as the control group and will not perform any exercises at all.

[figure not shown]

Figure 9: Back Training with Biofeedback

D8 3 1 Piloting Validation II Hospital.docx	Document Version: 1.0	Date: 2016-03-31	Status: For Approval	Page: 24 / 34
http://www.alfred.eu/	Copyright © ALFRED Project Consortium. All Rights Reserved. Grant Agreement No.: 611218			

Figure 10: Position of the Balance Boards

[figure not shown]

Figure 11: Screenshot of the 'Two Circles' Biofeedback

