#### 5.6.2. Risks and Other Demands to the Users

Potentially stressing factors to the study participants are the filling of the questionnaires, assessments and exercises during the study. These tests will take a maximum of 60 minutes and might be tiring or slightly exhausting. The pilot contains exercises which require muscular activity of medium intensity level. The exercises are conducted on a sport mattress or upon commercially available Nintendo Wii Balance Boards. The exercises are

D8 3 1 Piloting Validation II Hospital.docx	Document Version: 1.0	Date: 2016-03-31	Status: For Approval	Page: 29 / 34
http://www.alfred.eu/		Copyright © ALFRED Project Consortium. All Rights Reserved. Grant Agreement No.: 611218		

derived from exercises usually done in preventive lower back training sessions. The exercises are conducted and supervised by a trained member of the study personnel. The primary physical examination will take no more than one hour. The exercises themselves will not exceed 40 minutes per unit. After each task, there will be adequate breaks for the users to recover, their length being based on current scientific research and exercise physiology. Furthermore, each user may skip or terminate an exercise if deemed too exhausting, or for any other reason. The exercises might become more tiring and exhausting throughout the session. However, this is a normal process and inevitable to reach training progress. All users have the possibility to get water, if needed. If required, the study personnel may insert extra pauses to minimize the stress. Separate washing and changing rooms for male and female users are available.

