### 5.6.4. Predicted Medical Benefit for Future Diseased Persons

The goal of the study is the development of a new basic concept to implement biofeedback controlled exercises to strengthen trunk muscles and prevent LBP. For this purpose, the biofeedback training developed within the ALFRED project could be used as a new and more efficient training concept to prevent LBP in the future. One possible advantage could be a faster and more efficient training of the trunk musculature caused by the specific set training stimuli of the muscles of the lower back. These exercises might be able to restore the muscular stability of the lower back in a faster and more targeted way than in conventional exercises. Positive results of this study, combined with a high usability of the ALFRED back trainer, could lead to improved outcomes compared to the conventional preventive training of the lower back musculature.

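### CRB and CR differ in both support surface and visual feedback, so their contrast tests the whole Back Trainer system and cannot credit a difference to biofeedback alone.

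*Combined protocol and SAP*

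**What the plan says.** **Surfaces.** Section 5.6 (Visit 2-25) has the exercises "conducted on the floor with either a sport mattress (CR) or commercially available Nintendo Wii Balance Boards (CRB) which will provide biofeedback". Section 5.6.2 repeats the split: "The exercises are conducted on a sport mattress or upon commercially available Nintendo Wii Balance Boards". Section 5, which labels the same two arms CB and CBB, describes the biofeedback users as "lying on two commercially available Nintendo Wii Balance Boards (one underneath their shoulders and one underneath their feet", watching their movements on a tablet.

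**Intended contrast.** Section 5 says the biofeedback group "will perform identical exercises as the CB group, but with the additional perceived benefit of biofeedback training". Its hypothesis is that "the additional use of biofeedback during stabilizing exercises for the lower back will lead to increased LBP reduction", along with better daily function, strength and sleep. Visit 2-25 asks whether adding biofeedback, at the same amount of training, changes preventive factors, strength, everyday activities, balance and LBP. It also asks, as a secondary question, whether acceptance differs between the two groups.

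**A second framing.** The Executive Summary says the protocol was developed to compare the Back Trainer with exercises done without it. Section 4 sets the Back Trainer against conventional bridging and describes the distinction this way: "The main difference of the ALFRED Back Trainer and standard bridging exercises is that the user will additionally lie on two Nintendo Wii balance boards".

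**Third arm and analysis.** The control group performs no exercises (Section 5). Section 5.6.5 names only the software.

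**The concern.** If the exercises were identical and only the feedback were added, a difference between CRB and CR could be put down to feedback. Here the support under the shoulders and feet changes along with the display. A CRB advantage could come partly or wholly from training on boards. A CRB disadvantage, or no difference, could reflect difficulty on the boards that masks a useful feedback effect. The acceptance comparison has the same ambiguity, because a participant may like or dislike the boards rather than the feedback.

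What is at stake is the sentence D8.3.2 may write. Section 3.3.5 says that no existing study examines specific stabilising exercises for LBP combined with biofeedback devices. A positive result would therefore be read as first evidence on biofeedback, with no other study to correct the attribution.

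**Working it through.** There is no figure in the plan to reproduce. The documents give 60 participants, 20 per arm, with no alpha, power, effect size or SD. The check is whether the effect named in the hypothesis can be estimated from the arms that exist.

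**Step 1. Components by arm** (Sections 5, 5.6 and 5.6.2)

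| Arm | n | Exercises | Boards | Display |
|---|---|---|---|---|
| CR | 20 | yes | no (mattress) | no |
| CRB | 20 | yes | yes | yes |
| Control | 20 | no | no | no |
| *Boards, display off* | *none* | – | – | – |

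**Step 2. What the contrast estimates.** Let Y(boards, display) be the mean outcome under exercise.

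- Board effect: B = Y(1,0) − Y(0,0)
- Feedback effect, given the boards: F = Y(1,1) − Y(1,0)
- CRB − CR = Y(1,1) − Y(0,0) = F + B

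Randomisation identifies F + B. Separating the two requires Y(1,0), which no arm observes. The control group does not help because it does not exercise. Boards and display coincide perfectly across CR and CRB, so no covariate adjustment or model can separate them.

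**Step 3. Compare with the wording.** The comparison in the Executive Summary and Section 4 is F + B, which is estimable. The hypothesis in Section 5 and the question under Visit 2-25 are worded as F, which is not. Equating the two requires B = 0, and no passage states or supports that.

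**Step 4. Illustration only.** Assume F = 0, a standardised SD of 1, two-sided alpha 0.05, 20 per arm and a normal approximation. The chance of a significant result in favour of CRB is then Φ(B / √(2/20) − 1.96), with √(2/20) = 0.316.

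| Assumed B (SD units) | B / 0.316 − 1.96 | Probability |
|---|---|---|
| 0 | −1.960 | 0.025 |
| 0.2 | −1.328 | 0.09 |
| 0.3 | −1.011 | 0.16 |
| 0.5 | −0.379 | 0.35 |
| 0.8 | 0.570 | 0.72 |

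These values of B are invented to show how the attribution could fail; the documents supply none. B could also be zero or negative. If negative, it would hide a real feedback effect instead.

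**The case against.** The strongest reply is that the package is what the trial sets out to test. The Executive Summary and Section 4 say so, and the primary goal in Section 5.1 does not mention biofeedback. The boards are also the sensor: they supply the signal shown on the tablet, so biofeedback can be read as boards plus display. On that reading only the wording is inconsistent. Much of this stands. The package comparison is validly randomised, and Section 4's remark about the main difference is partly about sensing and is not an admission about surface. Section 5.6.4 is mostly system wording already; "the biofeedback training developed within the ALFRED project could be used as a new and more efficient training concept" names the developed product and is conditional. The reply does not remove the problem, because Section 5 speaks of identical exercises with biofeedback added, and a reader of D8.3.2 would take that as an effect of feedback.

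Three stronger readings are tempting and should be resisted.

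- **The surface is known to alter muscle activation.** A reader might infer this from a reference-list entry whose title compares stable and unstable bridging. Only the title is available, the protocol cites it for the role of the muscles, and nothing calls the boards unstable.
- **Firmness, lift range or discomfort differ materially.** The text describes no such difference. During the bridge the load is carried through shoulders and feet, which is where the boards lie, so the contact areas may be broadly similar on a mat.
- **CR must train on boards with the display off.** That would isolate feedback at the same 60 participants, but it gives up the conventional-training comparator that Section 4 and the acceptance question rely on. It is a design trade-off and not the correction of an error.

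**Conclusion.** The point holds as a limit on attribution. CRB versus CR estimates the effect of the whole Back Trainer system against conventional mat-based exercise. It cannot assign a difference to biofeedback alone, and the wording in Section 5 and under Visit 2-25 goes further than the design allows. The limit is structural and complete (20 of 20 CRB participants have both components, 0 of 20 CR participants have either), so a larger sample or a different analysis would not lift it.

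A reader might go on to infer that the trial is invalid, or that a CRB advantage would not be due to feedback. The documents support neither: randomisation protects the package comparison, and feedback may account for all of any difference. The size and direction of a board effect are unknown. The conclusion rests on the surfaces being as Sections 5.6 and 5.6.2 describe them, and on there being no display-off use of the boards, which no section mentions. The change should be made, since it settles what the trial may conclude and costs little.

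**What to change.** 1. In Section 5 and in Section 5.6 (Visit 2-25), restate the hypothesis and the CRB-CR question as *the Back Trainer system (boards plus display) versus conventional mat-based exercise*, in line with the Executive Summary and Section 4.
2. In Section 5, qualify the description of identical exercises by adding that the support surface also differs.
3. In Section 5.6.5, state that D8.3.2 will report CRB-CR differences, including those in acceptance, as effects of the system, and will not attribute them to biofeedback alone.

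**Cost.** The claim becomes narrower. Arms, sample size, visits and measurements are unchanged, and the document is still marked for approval, so the wording can be aligned before results are reported.
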